### **3.6.3.5 Overall Improvement / Overall Improvement and Stability**

Overall improvement rate will be analyzed, which is defined as the proportion of participants who have achieved an overall improvement as defined in Section 3.4.3 PRO Endpoints. Stratified Miettinen and Nurminen's method [Miettinen, O. and Nurminen, M. 1985] will be used for comparison of the overall improvement rate between the treatment groups. The difference in overall improvement rate and its 95% CI from the stratified Miettinen and Nurminen's method with strata weighting by sample size will be provided. The stratification factors used for randomization (Section 6.3.2 of the protocol) will be applied to the analysis.

The point estimate of overall improvement rate will be provided by treatment group, together with 95% CI using exact binomial method by Clopper and Pearson [Clopper, C. J. and Pearson, E. S. 1934].

[figure not shown]
The same method will be used to analyze overall improvement and stability rate, which is defined as the proportion of participants who have achieved overall improvement and stability as defined in Section 3.4.3 PRO Endpoints.

### **3.6.3.6 Analysis Strategy for Key PRO Endpoints**

A summary of the primary analysis strategy for key PRO endpoints is provided in [Table 7](#).

Table 7      Analysis Strategy for Key PRO Variables

CCI

### 3.6.4 Demographic and Baseline Characteristics

The comparability of the treatment groups for each relevant demographic and baseline characteristic will be assessed by the use of tables and/or graphs. No statistical hypothesis tests will be performed on these characteristics. The number and percentage of participants screened and randomized and the primary reasons for screening failure and discontinuation will be displayed. Demographic variables, baseline characteristics, primary and secondary diagnoses, and prior and concomitant therapies will be summarized by treatment either by descriptive statistics or categorical tables.

### 3.7 Interim Analyses

The eDMC will serve as the primary reviewer of the results of the IAs (including safety reviews) and will make recommendations for discontinuation of the study or modification to the executive oversight committee of the Sponsor. If the eDMC recommends modifications to the design of the protocol or discontinuation of the study, this executive oversight committee and potentially other limited Sponsor personnel may be unblinded to the treatment-level results in order to act on these recommendations. The extent to which individuals are unblinded with respect to results of IAs will be documented by the unblinded statistician. Additional logistic details are provided in the eDMC Charter.

Treatment-level results of the interim analysis will be provided by the unblinded statistician to the eDMC. Prior to final study unblinding, the unblinded statistician will not be involved in any discussions regarding modifications to the protocol or statistical methods, identification of protocol deviations, or data validation efforts after the IAs.

#### 3.7.1 Efficacy Interim Analyses

One IA is planned in addition to the FA for this study. For the IA and FA, all randomized participants will be included. Results of the IA will be reviewed by the eDMC. Details of the boundaries for establishing statistical significance with regard to efficacy are discussed further in Section 3.8.

The analyses planned, endpoints evaluated, and drivers of timing are summarized in [Table 8](#).

Table 8      Summary of Interim and Final Analyses Strategy

Analyses	Key Endpoints	Timing	Estimated Time after First Participant Randomized	Primary Purpose of Analysis
IA	OS (PFS and ORR if OS is rejected)	Both ~309 OS events have been observed and ~ 10 months after last participant randomized	~ 21 months	

• Interim OS analysis

• Final PFS and ORR analysis

FA	OS	Both ~386 OS events have been observed and ~ 12 months after IA	~ 33 months	

• Final OS analysis

Abbreviations: FA=final analysis; IA=interim analysis; ORR=objective response rate; OS=overall survival; PFS=progression-free survival.

Note that for FA, if the OS events accrual is slower than expected and the final targeted OS events cannot be reached by ~33 months after the first participant randomized, the Sponsor may conduct the analysis with up to additional ~4 months of follow-up, or the specified number of events is observed, whichever occurs first.

### 3.7.2 Safety Interim Analyses

[figure not shown]
The eDMC will be responsible for periodic interim safety reviews as specified in the eDMC charter. An interim safety analysis will be performed 6 months since first participant is randomized or 2 months after 60th participant is randomized, whichever comes first. Afterwards, the eDMC will review safety data periodically in the study. Interim safety analyses will also be performed at the time of interim efficacy analyses. Details are specified in the eDMC charter.

### 3.8 Multiplicity

The study uses the graphical method of Maurer and Bretz [Maurer, W. and Bretz, F. 2013] to provide strong multiplicity control for multiple hypotheses as well as interim analyses. According to this approach, study hypotheses may be tested more than once, and when a particular null hypothesis is rejected, the  $\alpha$  allocated to that hypothesis can be reallocated to other hypothesis tests. Note that if the OS null hypothesis is rejected at FA of the study, the previously computed PFS and ORR test statistics at IA may be used for inferential testing with its updated bounds considering the  $\alpha$  reallocation from the OS hypothesis. [Figure 1](#) shows the initial 1-sided  $\alpha$  allocation for each hypothesis in the ellipse representing the hypothesis. The weights for reallocation from each hypothesis to the others are shown in the boxes on the lines connecting hypotheses.

The initial  $\alpha$  assigned to OS, PFS and ORR will be 0.025, 0 and 0, respectively. If OS hypothesis is rejected, the corresponding alpha can be reallocated equally to PFS and ORR. If the PFS hypothesis is rejected, the corresponding alpha can be reallocated to ORR. If the ORR hypothesis is rejected, the corresponding  $\alpha$  can be reallocated to PFS.

Figure 1 Multiplicity Diagram for Type I Error Control

ORR=objective response rate; OS=overall survival; PFS=progression-free survival.

**Note:** If OS null hypothesis is rejected, the allocation strategy allows testing of PFS and ORR at  $\alpha = 0.0125$ , separately.

### 3.8.1 Overall Survival

The study will test OS at IA and FA. Following the multiplicity strategy as outlined in [Figure 1](#), the OS hypothesis will be tested at  $\alpha=0.025$ . [Table 9](#) shows the bounds and boundary properties for OS hypothesis testing derived using a Lan-DeMets spending function approximating O'Brien-Fleming bounds.

Table 9 Efficacy Boundaries and Properties for Overall Survival Analyses

Analysis	Value	$\alpha=0.025$
IA: 80%*	Z	2.2504
N: 432	$p$ (1-sided) a	0.0122
Events: 309	HR at bound b	0.7738
Month: 21	P(Cross) if HR=1 c	0.0122
	P(Cross) if HR=0.7 d	0.8123
FA	Z	2.0249
N: 432	$p$ (1-sided) a	0.0214
Events: 386	HR at bound b	0.8135
Month: 33	P(Cross) if HR=1 c	0.0250
	P(Cross) if HR=0.7 d	0.9350

Abbreviations: HR=hazard ratio; IA=interim analysis, FA=final analysis.  
 The number of events and timings are estimated.  
 \*Percentage of total planned events at the interim analysis.  
a $p$  (1-sided) is the nominal  $\alpha$  for group sequential testing.  
bHR at bound is the approximate HR required to reach an efficacy bound.  
cP(Cross if HR=1) is the probability of crossing a bound under the null hypothesis.  
dP(Cross if HR=0.7) is the probability of crossing a bound under the alternative hypothesis.

The bounds provided in the table above are based on the assumptions that the expected number of events at IA and FA are 309 and 386, respectively. At the time of an analysis, the observed number of events may differ substantially from the expected. To avoid overspending at an IA

and leave reasonable  $\alpha$  for the FA, the minimum  $\alpha$  spending strategy will be adopted. At an IA, the information fraction used in Lan-DeMets spending function to determine the alpha spending at the IA will be based on the minimum of the expected information fraction and the actual information fraction at each analysis. Specifically,

- In the scenario that the events accrue slower than expected and the observed number of events is less than the expected number of events at a given analysis, the information fraction will be calculated as the observed number of events at the IA over the target number of events at FA.
- In the scenario that the events accrue faster than expected and the observed number of events exceeds the expected number of events at a given analysis, then the information fraction will be calculated as the expected number of events at the IA over the target number of events at FA.

The final analysis will use the remaining Type I error that has not been spent at the earlier analysis. The event counts for all analyses will be used to compute correlations.

Of note, while the information fraction used for alpha spending calculation will be the minimum of the actual information fraction and the expected information fraction, the correlations required for deriving the bounds will still be computed using the actual information fraction based on the observed number of events at each analysis over the target number of events at FA.

The minimum spending approach assumes timing is not based on any observed Z-value and thus the Z test statistics used for testing conditioned on timing are multivariate normal. Given the probabilities derived with the proposed spending method, the correlations based on actual event counts are used to compute bounds that control the Type I error at the specified alpha level for a given hypothesis conditioned on the interim analysis timing. Since this is true regardless of what is conditioned on, the overall Type I error for a given hypothesis unconditionally is controlled at the specified level. By using more conservative spending early in the study, power can be retained to detect situations where the treatment effect may be delayed.

### 3.8.2 Progression-free Survival

The study will test PFS at IA only if the OS null hypothesis is rejected. Following the multiplicity strategy as outlined in [Figure 1](#), the PFS hypothesis may be tested at  $\alpha=0.0125$  (if the OS null hypothesis is rejected, but not the ORR hypothesis) or at  $\alpha=0.025$  (if both the OS and ORR null hypotheses are rejected). [Table 10](#) shows the boundary properties for each of these  $\alpha$  levels for the PFS analysis. Note that the final row indicates the total power to reject the null hypothesis for PFS at each  $\alpha$  level.

Table 10 Efficacy Boundaries and Properties for Progression-Free Survival Analysis

Analysis	Value	$\alpha=0.0125$	$\alpha=0.025$
IA N = 432 Events*: 419 Month: 21	Z	2.2414	1.9600
	$p$ (1-sided) a	0.0125	0.025
	HR at bound b	0.8032	0.8256
	P(Cross) if HR=1 c	0.0125	0.025
	P(Cross) if HR=0.65 d	0.9850	0.9929

Abbreviations: HR=hazard ratio; IA=interim analysis.  
\*The number of events and timing are estimated.  
a $p$  (1-sided) is the nominal  $\alpha$  for group sequential testing.  
bHR at bound is the approximate HR required to reach an efficacy bound.  
cP (Cross if HR=1) is the probability of crossing a bound under the null hypothesis.  
dP(Cross if HR=0.65) is the probability of crossing a bound under the alternative hypothesis.

Note that if the OS null hypothesis is rejected, the PFS test statistics computed at IA will be used for inferential testing with its corresponding alpha levels.

### 3.8.3 Objective Response Rate

The study will test ORR at IA only if the OS null hypothesis is rejected. Following the multiplicity strategy as outlined in [Figure 1](#), the ORR hypothesis may be tested at  $\alpha=0.0125$  (if the OS null hypothesis is rejected, but not the PFS hypothesis) or at  $\alpha=0.025$  (if both the OS and PFS null hypothesis is rejected). Power at the possible  $\alpha$ -levels as well as the approximate treatment difference required to reach the bound ( $\Delta$ ORR) are shown in [Table 11](#), assuming underlying 2% and 12% response rates in the control and experimental groups, respectively.

Table 11 Possible  $\alpha$  Levels and Approximate Observed ORR Difference Required to Demonstrate Efficacy for Objective Response at IA

$\alpha$	$\sim\Delta$ ORR	Power ( $\Delta$ ORR=0.1)
0.0125	0.0550	0.970
0.025	0.0481	0.984

IA=interim analysis; ORR=Objective Response Rate.

Note that if the OS null hypothesis is rejected, the ORR test statistics computed at IA will be used for inferential testing with its corresponding alpha levels.

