### 3. ANALYTICAL AND METHODOLOGICAL DETAILS

### 3.1 Statistical Analysis Plan Summary

Key elements of the statistical analysis plan are summarized below; the comprehensive plan is provided in Sections 3.2-3.12.

Study Design Overview	A Phase 3 study of MK-4280A Versus Standard of Care in Previously Treated Metastatic Colorectal Cancer.
Treatment Assignment	Approximately 432 participants will be randomized in a 1:1 ratio between 2 treatment groups: (1) the MK-4280A arm (Arm A) and (2) the standard of care (regorafenib or TAS-102) arm (Arm B). Stratification factors are: Geographic region (Asia Pacific; EMEA/Americas), presence of liver metastasis (Yes, No) and time from initial diagnosis of metastatic disease to randomization ( $\geq 18$ months, $< 18$ months). This is an open-label study.
Analysis Populations	Efficacy: ITT Safety: APaT
Primary Endpoint(s)	Overall survival
Key Secondary Endpoints	Progression-free survival per RECIST 1.1 as assessed by BICR. Objective response rate per RECIST 1.1 as assessed by BICR.
Statistical Methods for Key Efficacy/Immunogenicity/ Pharmacokinetic Analyses	The primary hypothesis testing for OS and secondary hypothesis testing for PFS will be evaluated by comparing the experimental group to the control group using a stratified log-rank test. The HR will be estimated using a stratified Cox regression model. Event rates over time will be estimated within each treatment group using the Kaplan-Meier method. The stratified M&N method with strata weighted by sample size will be used for secondary hypothesis testing of ORR [Miettinen, O. and Nurminen, M. 1985].
Statistical Methods for Key Safety Analyses	For analyses in which 95% CIs will be provided for between-treatment differences in the percentage of participants with events, these analyses will be performed using the M&N method [Miettinen, O. and Nurminen, M. 1985].
Interim Analyses	
Efficacy
 
One interim analysis is planned in this study. Results will be reviewed by an eDMC. Details are provided in Section 3.7.
 
 
• CCI
 
 
Safety
 
CCI

	will review safety data periodically in the study. Details will be specified in the DMC charter.

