### 3.6.1.3 Objective Response Rate

The stratified M&N method will be used for the comparison of ORR between 2 treatment groups [Miettinen, O. and Nurminen, M. 1985]. The difference in ORR and its 95% CI from the stratified M&N method with strata weighting by sample size will be reported. The stratification factors used for randomization (see Section 6.3.2 of the protocol) will be applied to the analysis.

The point estimate of ORR will be provided by treatment group, together with 95% CI using exact binomial method proposed by Clopper and Pearson [Clopper, C. J. and Pearson, E. S. 1934].

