### 3.6.1.5 Analysis Strategy for Key Efficacy Variables

A summary of the primary analysis strategy for the key efficacy endpoints is provided in [Table 3](#).

Table 3 Analysis Strategy for Key Efficacy Variables

Endpoint/Variable	Statistical Method	Analysis Population	Missing Data Approach
Primary Analysis			
OS	Testing: stratified log-rank test Estimation: Stratified Cox model with Efron's tie handling method	ITT	Censored at the date participant last known to be alive
Key Secondary Analyses			
PFS per RECIST 1.1 by BICR	Testing: stratified log-rank test Estimation: Stratified Cox model with Efron's tie handling method	ITT	Censored according to rules in Table 1
ORR per RECIST 1.1 by BICR	Testing and estimation: stratified M&N method	ITT	Participants with missing data are considered non-responders
Abbreviations: BICR=blinded independent central review; ITT=intent-to-treat; M&N=Miettinen & Nurminen; ORR=objective response rate; OS=overall survival; PFS=progression-free survival; RECIST 1.1=Response Evaluation Criteria in Solid Tumors.			

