### 3.9 Sample Size and Power Calculations

The study will randomize 432 participants in a 1:1 ratio into the MK-4280A arm (Arm A) and the standard of care arm (Arm B). OS is the primary endpoint for the study, with PFS and ORR as the key secondary endpoints.

For the OS endpoint, based on a target number of 386 events and 1 IA at approximately 80% of the target number of events, the study has approximately 93.5% power to detect a HR of 0.7 at the initially allocated  $\alpha=0.025$  (1-sided).

For the PFS endpoint, based on a target number of 419 events at the IA (final PFS analysis), the study has approximately 99% power to detect a HR of 0.65 at the reallocated  $\alpha=0.0125$  (1-sided) if only OS hypothesis is rejected.

Based on the 432 participants with at least approximately 10 months of follow-up, the power of the ORR testing at the reallocated  $\alpha=0.0125$  (1-sided) if only OS hypothesis rejected is approximately 97% to detect a 10-percentage point difference between an underlying 2% ORR in the control arm (Arm B) and a 12% ORR in the experimental arm (Arm A).

Note that the above OS and PFS power calculations are based on a constant HR assumption.

[figure not shown]
Based on CORRECT, RE COURSE, and SUNLIGHT studies (Section 4.2.1.1 of protocol), the above sample size and power calculations for OS and PFS assume the following:

- OS follows an exponential distribution with a median of 7.5 months for the control group.
- PFS follows an exponential distribution with a median of 2 months for the control group.
- Enrollment period of 12 months with enrollment ramp-up over first 2 months.
- An annual dropout rate of 2% and 5% for OS and PFS, respectively
- A follow-up period of 22 and 10 months and for OS and PFS, respectively, after the last participant is randomized.

The sample size and power calculations were performed using R (“gsDesign” package).

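### Does Table 11 overstate the observed ORR difference needed to demonstrate efficacy at the interim analysis?

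*SAP*

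**What the plan says.** Section 3.8.3 of the SAP introduces Table 11 as giving power and the "approximate treatment difference required to reach the bound", "assuming underlying 2% and 12% response rates in the control and experimental groups, respectively". The table prints 0.0550 with power 0.970 at alpha 0.0125, and 0.0481 with power 0.984 at alpha 0.025. The column header carries a tilde, and the title describes the entries as the "Approximate Observed ORR Difference Required to Demonstrate Efficacy for Objective Response at IA".

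The test is fixed elsewhere. Section 3.1 states "The stratified M&N method with strata weighted by sample size will be used for secondary hypothesis testing of ORR", section 3.6.1.3 repeats the method, and Table 3 in section 3.6.1.5 lists "Testing and estimation: stratified M&N method". Section 3.9 gives 432 participants randomized 1:1 and a power of "approximately 97% to detect a 10-percentage point difference between an underlying 2% ORR in the control arm".

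**The concern.** The title speaks of an observed difference, so a reader will take 5.50 or 4.81 points as what the data must show. The variance behind those values assumes a 7% average response rate. With a 2% control rate, a 7% average means an observed difference of 10 points, not 5.5. At a 2% control rate and a 5.5-point difference the average is 2% + 5.5%/2 = 4.75%, so the standard error is smaller and a smaller difference would reject. The section does not say that the required difference moves with the observed rates.

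The possible harm is that a result such as 4 versus 14 responders at alpha 0.0125 is read as falling short when the planned type of test would reject. The four decimals suggest more precision than the approximation has.

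**Working it through.** **Inputs.** 432 participants randomized 1:1, so 216 per arm (section 3.9). Planning rates 2% and 12%, average 7% (section 3.8.3). One-sided alpha 0.0125 or 0.025, so z = 2.2414 or 1.9600.

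**Reproducing Table 11.** The pooled standard error is sqrt(2 × 0.07 × 0.93 / 216) = 0.02455.

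- alpha 0.0125: 2.2414 × 0.02455 = 0.0550
- alpha 0.025: 1.9600 × 0.02455 = 0.0481

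Both match the table. The unpooled variance at 2% and 12% gives 0.0540 and 0.0472, which do not.

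Power on the same basis uses the unpooled standard error under the alternative, sqrt((0.02 × 0.98 + 0.12 × 0.88)/216) = 0.02408.

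- alpha 0.0125: Φ((0.10 − 0.0550)/0.02408) = 0.969
- alpha 0.025: Φ((0.10 − 0.0481)/0.02408) = 0.984

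These agree with the printed 0.970 and 0.984 to within 0.001.

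**Holding the control rate near 2%.** The unstratified Miettinen and Nurminen statistic for zero difference is Z = d / sqrt(2 p(1−p)/216 × 432/431), where p is the observed pooled rate. The smallest rejecting counts with 4 or 5 control responders are:

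| alpha | control v experimental | difference | Z | Z with one experimental responder fewer |
|---|---|---|---|---|
| 0.0125 | 4 v 14 | 4.6 points | 2.405 | 2.225 (fails) |
| 0.0125 | 5 v 15 | 4.6 points | 2.287 | 2.109 (fails) |
| 0.025 | 4 v 12 | 3.7 points | 2.036 | 1.837 (fails) |
| 0.025 | 5 v 14 | 4.2 points | 2.109 | 1.924 (fails) |

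A simulation with eight strata of assumed sizes gave the same thresholds.

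**Holding the total number of responders at its planned level.** The assumed rates imply 216 × 0.02 + 216 × 0.12 = 4.32 + 25.92 = 30.24 responders, a pooled rate of 7%.

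- alpha 0.0125, 30 responders: 9 v 21 is the least extreme split that rejects (Z = 2.269); 10 v 20 gives 1.890. The difference is 12/216 = 5.56 points.
- alpha 0.025, 31 responders: 10 v 21 rejects (Z = 2.048). The difference is 11/216 = 5.09 points. With exactly 30, 10 v 20 fails and 9 v 21 is again needed.

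The printed values correspond to 0.0550 × 216 = 11.9 and 0.0481 × 216 = 10.4 extra responders, which round up to 12 and 11. On this basis Table 11 is right to the nearest whole responder.

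**What misreading would cost.** Enumerating all outcomes under 2% v 12% and comparing a rule of the form difference ≥ value with the unstratified test:

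| alpha | value used as a rule | total disagreement | passes where the test fails |
|---|---|---|---|
| 0.0125 | 0.0550 (printed) | 0.94% | 0.10% |
| 0.0125 | 0.0463 (10 responders) | 0.79% | 0.77% |
| 0.025 | 0.0481 (printed) | 0.66% | 0.01% |
| 0.025 | 0.0417 (9 responders) | 0.35% | 0.33% |
| 0.025 | 0.0370 (8 responders) | 0.53% | 0.52% |

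The printed values err almost entirely on the conservative side; the smaller ones err almost entirely the other way. At a common response rate of 4% in both arms (an assumption for illustration), a fixed rule of 0.037 would have one-sided type I error of 3.3% against a nominal 2.5%, while 0.0481 would have 0.5%.

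**Power of the test itself.** Enumeration of the unstratified test under 2% v 12% gives 0.984 and 0.992, so the printed 0.970 and 0.984 are slightly conservative.

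**The case for a change.** The best case for a change is that the gap has a known direction and cause, so the word approximate does not fully excuse it. If the control rate truly is 2%, there will be at most 7 control responders with probability 93% and at most 8 with probability 97%. At those counts the smallest rejecting difference lies below the printed value for alpha 0.0125 and 0.025 respectively. The printed values fit a fixed control rate only at about 4.2% and 4.6%, more than twice the rate assumed. A footnote would cost almost nothing.

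The calculations stand. It is also fair that the word observed in the title invites a literal reading and that the dependence on the observed rates is not spelled out.

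The conclusion drawn from them does not stand. No single difference is correct for a score test, because the requirement moves with the observed rates. At alpha 0.0125 it runs from 5 extra responders when the control arm has none to 13 when it has 10. Fixing the control rate at 2% is one way to summarize that range; fixing the overall rate at the planned 7% is another, and the latter follows from the two rates the SAP states. Replacing the column would put one approximation in place of another, and the replacements would be no safer if misread. It would also separate the column from the powers derived on the same basis.

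**Conclusion.** No change is needed. Table 11 gives a planning approximation at the 7% pooled response rate implied by the stated 2% and 12%, and it reproduces exactly on that basis. The gap from the fixed-control-rate reading is about two responders at alpha 0.0125 (12 against 10) and two to three at alpha 0.025 (11 against 9 or 8). The stratified Miettinen and Nurminen p-value decides the ORR hypothesis, so the gap cannot alter a decision, the type I error or the sample size. The power figures in Table 11 and section 3.9 come from a normal approximation and are slightly conservative.

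An analyst will report the p-value and will not apply the column as a cut-off. A reader who wants the bar at particular observed rates can compute it directly.

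The conclusion rests on 216 participants per arm and on unstratified calculations, since the SAP does not give stratum sizes; the eight-strata simulation supports the thresholds but used assumed sizes.
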